5.2.2.4. Persistence and Half-life analysis of antibody level over time for infant subjects

This analysis is exploratory.

The decay of infant antibody levels over time will be analysed by a linear regression of the logarithm transformed of antibody levels. This analysis will be performed on PPS for infants in RSV vaccine group in terms of RSV-A neutralizing antibody titers, RSV-B neutralizing antibody titers and RSVPreF3 IgG-specific antibody concentrations.

CONFIDENTIAL209544 (RSV MAT-004)
Statistical Analysis Plan Amendment 3

A true, natural decay curve will be explored by stochastically reducing the sample to uninfected subjects only. The following steps will be taken to identify infected subjects (confirmed and suspected) to be eliminated from the sample:

- STEP 1: Infants with an RSV positive nasal swab during the study before time of blood sampling will be eliminated from the analysis because RSV infection may have contributed to their antibody levels which may no longer represent what was passively transferred from the mother.
- Infants whose mothers had an RSV positive nasal swab before or up to the time of delivery will be eliminated from the analysis. Maternal infection may contribute to post-vaccination increase in the levels of maternal antibodies, leading to higher placental antibody transfer to the fetus/infant, which would not reflect the effect of vaccination alone.
- STEP 2: Run the model and compute expected value based on the decay curve
- STEP 3: Subjects with an antibody titer at the blood sampling time that is more than 2-fold above the expected value based on their baseline (cord blood) value and the established decay curve will be considered to have been infected and then eliminated and the decay curve refined.
- STEP 4: Step 3 is repeated up to 5 times until the most accurate decay curve is established.

The natural decay of antibody level will be determined using linear regression between the logarithm transformed antibody level (Y) and time t (age in days) with subject as a random effect. All infants have RSV neutralizing antibodies measured at birth (cord blood) or within 3 days after birth, and each infant in PPS sub-cohort will have blood sampling for RSV neutralizing antibodies at one of the following time points: Day 43 post-birth, Day 121 post-birth or Day 181 post-birth. Therefore, in the natural decay model, each infant will have maximum 2 RSV neutralizing antibodies measures, one at birth or within 3 days after birth and the other at Day 43 post-birth, Day 121 post-birth or Day 181 post-birth depending on the sub-cohorts where the infants are.

The following SAS code will be explored:

```
PROC MIXED DATA=<filename>;
  CLASS PID;
  MODEL LOG_Y = t /s outp=pred;
  RANDOM Int t / sub=PID type=UN G GCORR;
RUN;
```

The choice of correlation structure and other parameters may be further adjusted according to the data and analysis needs.

The predicted value will be computed using the following formula

$$A_t = A_0 \exp(-K_e t)$$

where, A_t and A_0 are antibody titres at times t and zero, respectively, K_e is the constant rate of antibody change with time, defined as the estimate of model.

CONFIDENTIAL209544 (RSV MAT-004)
Statistical Analysis Plan Amendment 3

In addition, the half-life ($t_{1/2}$) of antibody (i.e. the time required for titre to decrease by one-half) will be displayed using the following equations of declining antibody titre:

$$\text{when } A_t = \frac{1}{2} A_0$$

$$t_{1/2} = 0.693 / K_e$$

A summary table will be prepared to show the number of infants included in the model, the model estimate of the antibody decay rate, and the half-life of the antibody.

In case cord blood samples are missing in 20% or more of infants in a single study group, separate analysis for infants with cord blood and infants with a blood sample within 3 days after birth will be performed.

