2090.Vx	Subjects did not comply with blood sample schedule – infant: 
 For infants without cord blood, check the interval from birth to Visit 1-NB birth BS = 0 – 3 days; For PPS at Day 43 post-birth, check the interval from birth to Day 43 BS = 28 – 60 days; For PPS at Day 121 post-birth, check the interval from birth to Day 121 BS = 110 –140 days; For PPS at Day 181 post-birth, check the interval from birth to Day 181 BS = 165 – 200 days 	Visit 1-NB/Birth Visit 2-NB/Day 43 post-birth Visit3-NB/Day 121 post-birth Visit4-NB/Day 181 post-birth	Immunogenicity
2100.Vx	Serological results not available	Visit 1-NB/Birth Visit 2-NB/Day 43 post-birth Visit3-NB/Day 121 post-birth Visit4-NB/Day 181 post-birth	Immunogenicity

CONFIDENTIAL209544 (RSV MAT-004)
Statistical Analysis Plan Amendment 3

Code	Condition under which the code is used	Visit (timepoints) where the code is applicable	Applicable for analysis set/endpoint
2120.Vx*	Obvious incoherence or abnormality or error in data	Visit 1-NB/Birth Visit 2-NB/Day 43 post-birth Visit3-NB/Day 121 post-birth Visit4-NB/Day 181 post-birth	Immunogenicity
2130.Vx	Testing performed on samples not aligned with ICF	Visit 1-NB/Birth Visit 2-NB/Day 43 post-birth Visit3-NB/Day 121 post-birth Visit4-NB/Day 181 post-birth	Immunogenicity
3100	Delivery happens less than 4 weeks post-vaccination.	All	Immunogenicity

*Attribution of these elimination codes to subject need CRDL review of individual listing

#Carry forward elimination from mother to infant

Vx+ indicates subjects whose immunogenicity data will be eliminated from a specific visit onwards; Vx indicates subjects whose immunogenicity data will be eliminated from a specific visit.

BS- Blood Sample.

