Section 4.2.3 Elimination from Per-protocol analysis set Table 5, Elimination code 2090.Vx Table 6, Elimination code 2090.Vx	Allowed intervals for completion of some visits (or contacts) have been widened.	Visit windows have been widened to promote data collection and data integrity during special circumstances (such as COVID-19).
Section 7.1.1, First analysis	Updates the Sequence of Analysis section to indicate that the first safety analysis will be by study group (rather than in aggregate) and performed by an independent statistician	Per U.S. FDA request
Section 9.1.2.1	Updated the assay cut-offs	Assay cut-offs are available after the release of lab immunogenicity data

CONFIDENTIAL209544 (RSV MAT-004)
Statistical Analysis Plan Amendment 2**2. OBJECTIVES/ENDPOINTS****Table 1 Study objectives and endpoints**

Primary Safety objectives	Primary Safety endpoint(s)
To evaluate the safety and reactogenicity of a single IM dose of study vaccine administered to maternal subjects, from Visit 1 up to 6 weeks after delivery	Occurrence of solicited administration site and systemic events during a 7-day follow-up period after vaccination (i.e. the day of vaccination and 6 subsequent days).
	Occurrence of any hematological (complete blood count with differential and platelet count) or biochemical (alanine amino-transferase, aspartate amino-transferase, creatinine, blood urea nitrogen) laboratory abnormality at baseline (up to 15 days before vaccination) and Day 8 (Visit 2)
	Occurrence of unsolicited AEs that occur during a 30-day follow-up period after vaccination (i.e. the day of vaccination and 29 subsequent days).
	Occurrence of serious adverse events (SAEs), AEs leading to study withdrawal, and medically attended AEs (MAEs) from Visit 1 (Day 1) up to 6 weeks after delivery (Day 43 post-delivery, Visit 6).
To evaluate pregnancy outcomes and pregnancy-related AESIs after a single IM dose of study vaccine administered to maternal subjects, from Visit 1 up to 6 weeks after delivery (Visit 6).	Pregnancy outcomes from Day 1 (Visit 1) up to 6 weeks after delivery (Day 43 post-delivery, Visit 6). These include live birth with no congenital anomalies, live birth with congenital anomalies, fetal death/still birth (antepartum or intrapartum) with no congenital anomalies, fetal death/still birth (antepartum or intrapartum) with congenital anomalies, elective/therapeutic termination with no congenital anomalies and elective/therapeutic termination with congenital anomalies.

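### The exploratory infant decay model uses actual age in days, yet its restriction to the PPS discards follow-up samples drawn outside the visit windows, at a small cost in precision and with no bias removed

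*SAP*

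**What the plan says.** Section 5.2.2.4 (Amendment 3) opens with "This analysis is exploratory" and fixes the analysis set: "This analysis will be performed on PPS for infants in RSV vaccine group". The model is a "linear regression between the logarithm transformed antibody level (Y) and time t (age in days) with subject as a random effect". The sample code has continuous time and no visit term. The section notes that an infant contributes at most two values: one at birth and one at Day 43, 121 or 181, according to subcohort.

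The windows are in section 4.2.3.2, Table 6, code 2090.Vx:
- "check the interval from birth to Day 43 BS = 28 – 60 days"
- "check the interval from birth to Day 121 BS = 110 –140 days"
- "check the interval from birth to Day 181 BS = 165 – 200 days"

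A footnote to that table explains that a Vx code removes the data of that visit only. Under code 2090.Vx an infant with a late or early follow-up sample therefore keeps the birth value and loses the follow-up value.

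The document history of SAP Amendment 2 shows that timing was a live issue: "Visit windows have been widened to promote data collection and data integrity during special circumstances (such as COVID-19").

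**The concern.** A visit window protects a summary that carries a nominal day. A geometric mean labelled Day 181 should not mix in a sample from day 215. A regression on actual age needs no such protection, because a sample from day 75, 150 or 215 enters at its true position on the time axis.

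The design makes each loss complete. With one follow-up sample per infant, removing it leaves no within-infant slope, and the birth value alone adds almost nothing to the decay rate. The analysis would thus discard slope information the trial has already collected, for a reason that belongs to other tables. What is at stake is the precision of the half-life estimate.

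**Working it through.** **The SAP's own figure.** Setting A_t = A_0/2 in A_t = A_0·exp(−K_e·t) gives t½ = ln 2 / K_e. Since ln 2 = 0.6931, the constant 0.693 in 5.2.2.4 is reproduced. The SAP states no sample size or precision target for this analysis.

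**Inputs.** The SAP gives the windows, the use of age in days and the maximum of two samples per infant. The document history of Amendment 2 gives 213 vaccinated women; two thirds is 142 in the two vaccine groups, or about 47 infants per subcohort if all contribute.

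Assumed, because the SAP is silent:
- 5%, 10% or 20% of follow-up samples are out of window;
- these are either all late (days 75, 150, 215) or all early (days 22, 105, 160);
- half-life 35–60 days, residual SD 0.3–0.5 log2, between-infant CV of the slope 0–20%.

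**Precision, closed form.** An infant sampled at birth and at age t has a difference with variance t²τ² + 2σ², where τ is the between-infant slope SD and σ the residual SD. Its slope information is t²/(t²τ² + 2σ²). With τ = 0, σ cancels, and for an excluded share f

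SE ratio = √(1 + [f/(1 − f)]·B/A),

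where A sums t² over the nominal days and B over the out-of-window days:
- A = 43² + 121² + 181² = 49,251
- B late = 75² + 150² + 215² = 74,350, so B/A = 1.510
- B early = 22² + 105² + 160² = 37,109, so B/A = 0.753

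For f = 0.10, late: √(1 + 0.1111 × 1.510) = 1.081. Early: √(1 + 0.1111 × 0.753) = 1.041.

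Letting the slope CV run from 0 to 20% gives these increases in the SE of the decay rate, compared with keeping the samples:

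| Share out of window | All late | All early |
|---|---|---|
| 5% | 3.1–3.9% | 2.0–2.2% |
| 10% | 6.5–8.1% | 4.1–4.6% |
| 20% | 14.0–17.4% | 9.0–10.2% |

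**Cross-check.** The second calculation uses the full random intercept and slope model with 142 infants, a half-life of 45 days, natural-log SDs of 0.9 (intercept), 0.003 per day (slope) and 0.35 (residual), and late samples at days 75, 152 and 212. It gives increases of 2.7%, 7.2% and 14.8%.

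**In days.** With K_e = 0.6931/45 = 0.0154 per day, SE(t½) ≈ 45 × SE(K_e)/K_e. In the cross-check model:
- 10% out of window: SE(K_e) is 0.000437 with the samples kept and 0.000468 without, so SE(t½) is 1.28 against 1.37 days, a difference of 0.09 day.
- 20% out of window: 0.000431 against 0.000494, so 1.26 against 1.44 days, a difference of 0.19 day.

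**Bias.** In 1,000 simulated trials with a true half-life of 45 days and 10% of samples late, the mean-slope half-life was 44.98 days with the samples dropped and 44.98 days with them kept at actual age. Entering them at the nominal day would have biased it to 43.90 days, but the SAP specifies age in days, so the windows are not needed to prevent that.

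**The case against.** The strongest reply is that the loss is too small to matter. The analysis is exploratory, SAP section 6 makes all comparisons descriptive, no decision rests on the half-life, and the cost is a fraction of a day. The windows were already widened, so few samples may fall outside them. All of this stands, and it sets the priority.

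Section 5.2.1 also provides a complementary Full Analysis Set analysis when 5% or more of vaccinated subjects with serology are excluded from the PPS in any group at any timepoint. Its infant table lists half-life modelling, and FAS Table 4 has no code 2090. That may mitigate the loss. It does not settle the point, because 5.2.2.4 names only the PPS, and the FAS would lift every other PPS exclusion as well.

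Three stronger readings might be inferred and are not supported:
- *The excluded samples carry the most leverage.* This holds only if they are late. Samples before day 28, for example, are excluded too and carry little.
- *The single exponential cannot be checked.* In-window data already give four age clusters (birth, 28–60, 110–140 and 165–200 days), enough to look for curvature.
- *The Step 1 rule on mothers is also wrong:* "Infants whose mothers had an RSV positive nasal swab before or up to the time of delivery will be eliminated from the analysis". The half-life formula has no A_0 term, so a higher start seems irrelevant. But the SAP states a purpose, a curve reflecting vaccination alone. The section also covers persistence and predicts levels from A_0, and its unstructured random effects let intercept and slope correlate. No gain from deleting the rule was shown: with 5% of mothers positive and a three-fold higher start, the simulated half-life was 44.98 days with these infants kept and 44.97 without. PPS code 2060#* for maternal infection could remove the same infants anyway.

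**Conclusion.** The point holds as a matter of efficiency. Applying code 2090.Vx to a model in actual age removes no bias under the SAP's constant-rate model and discards the only slope-bearing sample of each affected infant. The increase in the standard error of the decay rate is about 2–4%, 4–8% and 9–17% at 5%, 10% and 20% out of window, with the lower ends for early and the upper ends for late samples. This rests on assumed shares, timings and variances; the true share could be below 5%, in which case the loss is smaller still.

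A reader should not infer that the planned half-life is biased or that any conclusion of the trial is at risk. Priority: minor.

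**What to change.** In section 5.2.2.4, state that the analysis is performed on PPS infants except that code 2090.Vx is not applied to follow-up samples, which enter the model at their actual age in days. Add a footnote to the half-life table saying that this set differs from the PPS used for the GMT/GMC tables.

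Keep both Step 1 exclusions, for infants with their own earlier positive swab and for infants of RSV-positive mothers. At most, add a sensitivity analysis that retains the infants of RSV-positive mothers; it must also waive code 2060#*, or the same infants may still be missing.

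The cost is one sentence and a footnote. No new data are needed, and the GMT/GMC tables do not change.

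### In the infant decay analysis, repeated deletion of only the infants more than 2-fold above the curve shortens the half-life among uninfected infants, and no untrimmed fit is required beside it

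*SAP*

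**What the plan says.** SAP Amendment 3, section 5.2.2.4, sets out four steps for infants in the RSV vaccine group of the per-protocol set.

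- Step 1 handles confirmed infection: "Infants with an RSV positive nasal swab during the study before time of blood sampling will be eliminated from the analysis". Infants of mothers with a positive swab up to delivery are also removed.
- Step 2 fits the decay model and computes expected values.
- Step 3 labels as infected every infant whose titre is "more than 2-fold above the expected value based on their baseline (cord blood) value and the established decay curve will be considered". Those infants are then dropped and the model is fitted again without them.
- Step 4 reads: "Step 3 is repeated up to 5 times until the most accurate decay curve is established". The section does not define what makes a curve most accurate.

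On the data and model, "each infant will have maximum 2 RSV neutralizing antibodies measures": one at birth and one at Day 43, 121 or 181. The sample code has "RANDOM Int t / sub=PID type=UN G GCORR", so it allows infants to differ in decay rate. On output: "A summary table will be prepared to show the number of infants included in the model, the model estimate of the antibody decay rate", together with the half-life. The section opens with "This analysis is exploratory".

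**The concern.** Step 3 selects on the outcome, in one direction, among infants with no positive swab of their own before sampling and none in the mother up to delivery. The expected value rests on one cord reading, so error in both samples enters the comparison. A slow decay rate, which the model itself allows, is read as infection. Infants equally far below the curve stay in. Each deletion steepens the fitted curve and lowers the expected values, so more infants cross the line at the next pass.

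The section presents the result as the natural decay curve, free of infection. The only table it requires shows the final fit, so a reader could not tell how far the deletions had moved the half-life. Half-life modelling is also listed among the secondary infant immunogenicity methods in section 5.2.1.

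**Working it through.** **The plan's own figure.** The half-life is 0.693 / Ke, and ln 2 = 0.6931, so the constant is right. The section gives no assay SD, decay-rate spread, expected half-life or rate of missed infection. Those values below are assumptions.

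**Sample size.** The Amendment 2 document history reports 213 vaccinated women. 213 / 3 = 71 per group, simulated as 72 infants (24 per sampling day). The two vaccine groups together were simulated as 141 (47 per day).

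**Chance that an uninfected infant crosses the line at the first pass.** Let s be the SD of ln(observed/expected). The chance is P(Z > 0.693 / s):

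| s | 0.2 | 0.3 | 0.4 | 0.5 | 0.6 | 0.8 |
|---|---|---|---|---|---|---|
| chance | 0.03% | 1.0% | 4.2% | 8.3% | 12.4% | 19.3% |

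With assay SD σ per sample (ln scale) and coefficient of variation CV for the decay rate, s² = 2σ² + (CV × k × t)². For a half-life of 40 days, k = 0.693 / 40 = 0.0173 per day. Take σ = 0.3 and CV = 15%:

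- Day 43: s = √(0.180 + 0.0125) = 0.44, chance about 6%
- Day 121: s = √(0.180 + 0.099) = 0.53, chance about 9%
- Day 181: s = √(0.180 + 0.221) = 0.63, chance about 14%

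The rise with age comes from decay-rate spread. With CV = 0, s = 0.42 and the chance is about 5% on every day.

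**Full algorithm, no infection, true half-life 40 days.** Expected value = own cord value × exp(-Ke t). Infants above 2-fold are deleted and the model refitted, with up to five rounds or repeats. Each scenario has 800 or 1000 simulated trials. SDs given as log10 are multiplied by 2.303.

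| infants | ln SD per sample | CV | deleted | half-life (days) | change |
|---|---|---|---|---|---|
| 72 | 0.10 | 0% | 0% | 40.0 | nil |
| 72 | 0.15 | 10% | 1.6% | 39.7 | -1% |
| 141 | 0.23 (log10 0.10) | 5% | 2.5% | 39.6 | -1% |
| 72 | 0.30 | 10% | 10% | 38.3 | -4% |
| 141 | 0.30 | 15% | 15% | 37.1 | -7% |
| 141 | 0.35 (log10 0.15) | 15% | 20% | 36.3 | -9% |
| 72 | 0.40 | 20% | 30% | 33.7 | -16% |
| 141 | 0.46 (log10 0.20) | 20% | 37% | 32.4 | -19% |

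Without Step 3 the same data give 40.0 days.

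**Cause.** With 141 infants, SD 0.30 and CV 15%, one pass gives 38.1 days and all passes 37.1, so repetition adds to the bias. A symmetric 2-fold rule gives 40.0 in that setting, so the one-sidedness is what does it. Under random-intercept and within-infant fits, deletion lengthened the half-life in no run. With SD 0.30 and CV 15%, true half-lives of 30, 50 and 60 days become 27.5, 46.7 and 56.3.

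**With infections that the swabs miss, true half-life 40 days.**

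| undetected, boost | noise | without Step 3 | SAP rule |
|---|---|---|---|
| 5-20%, 2- to 10-fold | ln SD 0.30, CV 10% | 40.5-46.8 | 38.2-38.9 |
| 5-20%, 2- to 10-fold | ln SD 0.15, CV 5% | 40.4-46.9 | 39.9-40.9 |
| 10%, 4-fold | log10 SD 0.10, CV 5% | 43.0 | 39.7 |
| 10%, 10-fold | log10 SD 0.15, CV 15% | 45.1 | 36.3 |

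**Limit of the check.** The fits used a random intercept or a within-infant slope. The random-slope code in the SAP, which calls itself open to adjustment, was not simulated.

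**The case against.** The rule has a purpose. Infection raises titre, so a screen on the upper side is a reasonable way to find infections that swabs miss, and keeping infants below the curve is deliberate. How many are missed depends on swab rules in the protocol, which is not at hand. The second table shows that the rule can do its job: at low noise it ends near the truth, while the fit without it is too long.

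The stakes are also limited. The analysis is exploratory and no decision rule uses the half-life. Section 5.2.1 still reports untrimmed geometric means with 95% CIs and reverse cumulative curves at every infant timepoint. The number of infants in the model is tabulated, so heavy trimming would leave a trace.

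These points stand, and they rule out three stronger readings that a reader might infer.

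- That the reported half-life must be too short. The net bias depends on noise and missed infection, and the SAP states neither.
- That the Step-1-only fit should replace the trimmed one. This could exchange a downward bias for a larger upward one: in the last row above, +13% against -9%.
- That the trimmed fit will look too precise. The section lists no standard error or confidence interval.

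The gap in the output remains: the tabulated N does not show how many infants Step 3 removed, at which ages, or what the half-life was before.

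**Conclusion.** As written, Steps 3 and 4 shorten the half-life among uninfected infants. That direction follows from the text. The size does not: with no undetected infection and an assumed true half-life of 40 days, it runs from nil at very low noise to about -19%, with 36 to 37 days at moderate noise. If infections are missed, the untrimmed fit reads about 40.5 to 47 days under the assumptions tried, and the SAP rule comes close to the truth only at low noise. Neither fit alone supports a claim to the natural decay curve. Because the analysis is exploratory, no primary conclusion is affected. It is still worth correcting, because the planned table hides a shift that could reach several days.

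**What to change.** In the section 5.2.2.4 summary table, report two fits side by side as bounds: the Step-1-only fit (swab-based exclusions, no titre-based deletion) and the trimmed fit. Add the number deleted at each pass and sampling day. Do not describe the trimmed curve alone as the natural decay.

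If a suspected-infection rule is kept, one option is a single pass at an age-specific upper 99% prediction limit from the model, combining residual and slope variance. That would hold false deletions to about 1%. Its downsides are that it leaves some real infections in, and that the slope variance is weakly estimated with at most two samples per infant.

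The cost is SAP wording and one extra model fit. No new data are needed.

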Infant subjects	
 • RSVPreF3 IgG-specific antibody concentration • Neutralising antibody titres against RSV-A • Neutralising antibody titres against RSV-B 
For all 3 RSV-specific antibody assessments: measured in a subcohort of infants at Day 43 after birth (sub-cohort V2-NB), in a subcohort of infants at Day 121 (sub-cohort V3-NB) after birth and in a subcohort of infants at D181 after birth (sub-cohort V4-NB). Each infant will be randomly assigned to 1 of
	
For each assay, at each timepoint and by study group
 
 • Antibody titres/concentrations will be displayed using reverse cumulative curves. • GMTs/ GMCs will be tabulated with 95% CI and represented graphically. 
In addition, analyses will include exploratory evaluation of the persistence of RSV specific antibodies in infants through time, and half-life analysis modelling of logarithm transformed RSV antibody concentrations/titers over time.
 
Between group evaluation on vaccine formulations in terms of RSVPreF3 IgG-specific antibody concentrations / neutralizing antibody titers will be performed on cord blood at Delivery, and on blood samples collected at 6 weeks, 4 months and 6 months post-birth using a mixed effect model on the logarithm₁₀ transformation of the concentrations/titers,

CONFIDENTIAL209544 (RSV MAT-004)
Statistical Analysis Plan Amendment 3

	Secondary Immunogenicity Endpoints	Statistical Analysis Methods

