5.2.2.3. Between group analysis

This analysis is exploratory.

For the analysis of maternal subjects at each time point (Day 31, Delivery, and Day 43 post-delivery), the model will be explored and fitted via the proc mixed procedure according to the following code:

```
PROC MIXED data=sero;
  CLASS /*subjid*/ group ges_age_cat age_cat center;
  MODEL log_val = baseline group ges_age_cat age_cat
inter_vac_del center /ddfm=kenwardroger outp = pred;
  /*RANDOM Subjid*/;
  LSMEANS group/pdiff cl alpha=0.05;
RUN;
```

where log_val represents the log-transformed antibody value of the immunogenicity variable at a given post baseline timepoint, group indicates the study group, ges_age_cat is the gestational age category at vaccination ($28^{0/7}$ - $31^{0/7}$, $31^{1/7}$ - $33^{6/7}$ weeks), age_cat is the age category at vaccination (18 – <35 years and \geq 35 years), inter_vac_del is the interval between vaccination and delivery (days). The inclusion of age category at vaccination, interval between vaccination and delivery, and center in the model depends on the availability of the variable (inter_val_del may not be available at Day 31 analysis) and the necessity, therefore, the above SAS code serves as a reference and may be adjusted according to the analysis needs.

CONFIDENTIAL209544 (RSV MAT-004)
Statistical Analysis Plan Amendment 3

For the analysis of infants at each time point (cord blood at Delivery, Day 43 post-birth, Day 121 post-birth, and Day 181 post-birth), similar model will be explored:

```
PROC MIXED data=sero;
  CLASS /*subjid*/ group center ges_age_cat ges_age_birth;
  MODEL log_val = baseline group ges_age_cat /*inter_vac_del*/
  ges_age_birth center /ddfm=kenwardroger outp = pred;
  /*RANDOM Subjid*/;
  LSMEANS group/pdiff cl alpha=0.05;
  RUN;
```

Baseline is pre-vaccination logarithm10 transformation of the concentrations/titers from maternal subjects, ges_age_birth is gestational age category at birth (> 37 weeks; ≤ 37 weeks) for infants. With the inclusion of gestational age category at vaccination (ges_age_cat) in the model, this categorical variable ges_age_birth provides similar information as continuous variable inter_vac_del, therefore the inclusion of either variable in the model could be adjusted according to the analysis needs.

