The ratio of GMTs/GMCs between vaccine groups and the corresponding 95% CI will then be constructed by exponentiating the mean difference and its confidence interval between vaccine groups on the logarithm10 scale estimated from the model. Summary tables will show adjusted GMT/GMC for vaccine groups, and ratios of GMTs/GMCs between vaccine groups along with the 95% CI.

If deemed necessary, an analysis of variance model for repeated measures will be fitted to assess the mean profile in each group over time for both maternal and infant subjects separately. Below is the sample SAS code for the analysis of maternal subjects, and similar codes could be explored for the analysis of infants.

```
PROC MIXED data=sero;
  CLASS subjid group visit age_cat center ges_age_cat;
  MODEL log_val = baseline group | visit age_cat ges_age_cat
  inter_vac_del center/ddfm=kenwardroger outp = pred;
  RANDOM subjid;
  /*REPEATED visit/subject=subjid(group) type=un;*/
  LSMEANS group*visit/pdiff cl alpha=0.05;
  RUN;
```

Summary tables will present adjusted GMT/GMC with 95% CI for each group at each timepoint.

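### Section 5.2.2.4 sets the decay constant equal to the fitted slope, so the half-life is negative as written; the log base is also unstated, and a log10 fit would add a 2.3-fold error

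*SAP*

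**What the plan says.** SAP section 5.2.2.4 opens: "The decay of infant antibody levels over time will be analysed by a linear regression of the logarithm transformed of antibody levels". Its modelling paragraph describes a "linear regression between the logarithm transformed antibody level (Y) and time t (age in days) with subject as a random effect", and the sample code is "MODEL LOG_Y = t /s outp=pred" with a random intercept and a random slope per infant. Neither the text nor the code gives the base of the logarithm.

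The section then computes predicted values from A_t = A_0 exp(−K_e t) and the half-life from t1/2 = 0.693/K_e. It defines the constant in one sentence: "K_e is the constant rate of antibody change with time, defined as the estimate of model". No change of sign and no conversion factor is given.

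The predicted value is more than a display item. In Steps 2 to 4, infants whose level exceeds twice the expected value (from their cord-blood level and the decay curve) are treated as infected and removed. The curve is then refitted, up to five times. The decay rate and the half-life both go into a summary table.

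Elsewhere, where the SAP names a base, it is 10. In section 5.2.2.3 the group ratios are "constructed by exponentiating the mean difference and its confidence interval between vaccine groups on the logarithm10 scale", and for the infant model "Baseline is pre-vaccination logarithm10 transformation of the concentrations/titers from maternal subjects". The secondary-endpoint table in section 5.2.1 lists "half-life analysis modelling of logarithm transformed RSV antibody concentrations/titers over time" without a base, in the same cell that specifies log10 for the between-group model.

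**The concern.** Two things do not fit together. The first is the sign. The decay equation already carries a minus sign, so K_e must be positive, but the model estimate for t is a signed slope and is negative whenever antibody declines.

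The second is the scale. The functions exp() and 0.693 = ln 2 belong to the natural logarithm, and the section never says that LOG_Y is on that scale. The same infant data are analysed on the log10 scale one section earlier, so a programmer could reuse that variable.

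At stake are the reported decay rate and half-life, and the Step 3 eliminations, which depend on the same K_e. A negative half-life would be noticed. A positive half-life inflated by a constant factor might not be.

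**Working it through.** **Inputs.** From section 5.2.2.4: the model LOG_Y = intercept + b·t, the prediction A_t = A_0 exp(−K_e t), the half-life 0.693/K_e, and the rule K_e = b. The SAP gives no half-life, so true values of 30, 40, 50 and 60 days are assumed.

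**The SAP's own constant.** Setting A_t = A_0/2 gives exp(−K_e t) = 1/2, so t1/2 = ln(2)/K_e = 0.6931/K_e. The figure 0.693 is right, provided K_e is positive and on the natural-log scale.

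**What the regression estimates.** With natural log, b = −K_e. With log10, b = −K_e/ln(10) = −K_e/2.303.

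**Sign, rule taken literally (K_e = b), true half-life 40 days.**
- Natural log: b = −0.6931/40 = −0.01733. Half-life = 0.693/(−0.01733) = −40.0 days. The predicted fraction of the cord level is exp(0.01733·t) = 2.1, 8.1 and 23.0 at t = 43, 121 and 181, against true fractions of 0.475, 0.123 and 0.043. At Day 181 an infant would have to exceed 2 × 23.0 = 46 times its cord level to be flagged, so Step 3 would have almost no effect.
- Log10: b = −0.3010/40 = −0.00753. Half-life = 0.693/(−0.00753) = −92.1 days. The predicted fractions are 1.4, 2.5 and 3.9, so they also rise.

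The sign therefore fails on either base.

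**Scale, sign corrected but a log10 slope used.** The half-life becomes 0.693/(−b), and the Step 3 expected value is exp(b·t) instead of 10^(b·t).

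| Assumed true half-life (days) | log10 slope b | 0.693/(−b) (days) | Expected value too high by, Day 43 | Day 121 | Day 181 |
|---|---|---|---|---|---|
| 30 | −0.01003 | 69.1 | 1.75 | 4.86 | 10.65 |
| 40 | −0.00753 | 92.1 | 1.52 | 3.27 | 5.90 |
| 50 | −0.00602 | 115.1 | 1.40 | 2.58 | 4.13 |
| 60 | −0.00502 | 138.1 | 1.32 | 2.21 | 3.26 |

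The half-life ratio is 2.30 in every row, which is ln(10). For a true 40 days, the Day 181 expected value is 0.256 of cord instead of 0.043. The 2-fold rule then acts as a 2 × 5.90 = 11.8-fold rule (6.5-fold to 21.3-fold over the assumed range). Infected infants would tend to stay in and flatten the curve.

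**Corrected formulas.** K_e = −b (natural log), or K_e = −2.303·b, equivalently t1/2 = −0.301/b (log10), return 30, 40, 50 and 60 days.

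**Check by simulation.** 200 infants were simulated with two samples each (birth plus one of Days 43, 121 or 181), a true half-life of 45 days and a random-intercept fit. The natural-log slope was −0.01537, so 0.693/b = −45.1 days. The log10 slope was −0.00667, so 0.693/(−b) = 103.8 days and 0.301/(−b) = 45.1 days.

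**The case against.** The strongest reply is that the section is coherent if read as a whole. It writes a decay equation with an explicit minus sign, speaks of declining titres and reports a decay rate, so K_e is evidently meant to be positive. Its formulas are natural-log formulas. The SAP writes log10 explicitly when it means log10, and section 5.2.1 uses the plain wording and the log10 wording side by side in one cell, which suggests that the difference is deliberate. On that reading the size of the half-life is exactly right. A negative half-life is also unlikely to survive programming, and the analysis is labelled exploratory, with code that may be adjusted.

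Much of this stands. A reader might infer that the plan will report a half-life 2.3 times too long, or that its infection screen will be wrong by the factors in the table. The SAP does not support that, because section 5.2.2.4 never says log10 and natural log is the more consistent reading.

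Two things remain. The sentence that defines K_e is wrong on either base, and the surrounding wording shows what was intended without stating it. The base is left to inference when the same data are modelled on log10 under a variable also labelled only as a log value, so reuse is a realistic slip. The permission to adjust the correlation structure and other parameters concerns the model fit, not the definition of K_e. The wording is the same in all four SAP versions supplied.

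**Conclusion.** The definition of K_e is wrong as written. For declining antibody it gives a negative half-life and rising expected values in Steps 2 and 3, regardless of log base. This needs no assumption beyond antibody declining, and it would probably be noticed.

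The unstated base is a separate and conditional risk. Under natural log only the sign needs correcting. Under log10, with the sign corrected, the half-life is 2.3 times too long. The 69 to 138 days quoted for that case rest on assumed true half-lives of 30 to 60 days, and so does the 3.3-fold to 10.7-fold excess in the Day 181 expected value.

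The consequence is limited to the exploratory decay rate, the half-life and the Step 3 eliminations. No primary endpoint depends on it. It should be corrected because the rule itself is wrong and the repair is trivial.

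**What to change.** In section 5.2.2.4, state that LOG_Y is the natural logarithm of the titre or concentration and that K_e = −(fixed-effect slope of t), so t1/2 = 0.693/K_e holds as printed. If log10 is preferred for consistency with the between-group models, define K_e = −2.303 × slope, equivalently t1/2 = −0.301/slope. State that the same K_e is used for the expected values in Steps 2 and 3 and for the decay rate in the summary table. The cost is one line of SAP text and a check of the program; the data and the model stay as they are.
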